10.4	INFORMED CONSENT PROCESS / HIPAA AUTHORIZATION	23
11	STUDY FINANCES	23
11.1	FUNDING SOURCE.....	23
11.2	CONFLICT OF INTEREST	23
11.3	SUBJECT STIPENDS OR PAYMENTS	23
12	REFERENCES	24
13	ATTACHMENTS	29

CONFIDENTIAL

This material is the property of the University of Pennsylvania.

List of Abbreviations

adverse event (AE)
analysis of functional neuroimages AFNI
anxiety potentiated startle (APS)
anxiety-potentiated-BOLD AP-BOLD
bed nucleus of the stria terminalis (BNST)
case report form (CRF)
central nervous system (CNS)
cognitive paired-associate stimulation (C-PAS)
continuous theta-burst stimulation (cTBS)
dorsolateral prefrontal cortex (dlPFC)
electromyographic (EMG)
echo planar imaging (EPI)
Ethics Committee (EC)
Food and Drug Administration (FDA)
Fear potentiated startle (FPS)
first dorsal interosseus (FDI)
fear-potentiated-BOLD (FP-BOLD)
Health Insurance Portability and Accountability Act of 1996 (HIPAA)
high-frequency rTMS (HF-rTMS)
independent components analysis (ICA)
intermittent theta-burst stimulation (iTBS)
intertrial interval (ITI)
low-frequency rTMS (LF-rTMS)
motor evoked potential (MEP)
motor threshold (MT)
magnetic resonance imaging (MRI)
National Institute for Neurological Disorders and Stroke (NINDS)
neutral (N)
neutral predictable unpredictable threat task (NPU)
principle investigator (PI)
predictable shock (P)
protected health information (PHI)
repetitive TMS (rTMS)
serious adverse event (SAE)
echo time (TE)
Beck Anxiety Inventory (BAI)
State Anxiety Scale (S-Anxiety)
transcranial magnetic stimulation (TMS)
TMS adult safety screen (TASS)
Theta-burst stimulation TBS
unanticipated problem (UP)
unpredictable shock (U)
working memory (WM)

CONFIDENTIAL

Study Summary

Title Examining the mechanisms of anxiety regulation using a novel, sham-controlled, fMRI-guided rTMS protocol and a translational laboratory model of anxiety.

Short Title Effect of rTMS on anxiety

IRB Number 833320

Phase Pilot Study

Methodology Randomized, double-blinded, sham-controlled, cross-over design

Study Duration 4 years

Study Center(s) Single-center

Objectives

Aim 1: Determine the effect of a 1-week course of TBS treatment (Continuous vs. Intermittent; right dIPFC target) on anxiety using the unpredictable shock-threat paradigm.

Aim 2: Determine the effect of a 1-week course of TBS treatment (Continuous vs. Intermittent; right dIPFC target) on anxiety-related WM-deficits using the Sternberg WM paradigm during threat of shock.

Aim 3: Demonstrate target engagement by measuring BOLD responses evoked by TMS pulses to the right dIPFC during threat of shock.

Number of Subjects 75

**Main Inclusion
and Exclusion
Criteria**

Healthy volunteers, between 18 – 50 years old, free of psychological and neurological conditions, free of contraindications for TMS and MRI

Aim 1: Outcome measures. Fear potentiated startle (FPS) and Anxiety potentiated startle (APS) Statistical Analysis. The main analysis will be a 3 [stimulation: pre-stimulation vs. post-active vs. post-sham] by 2 [protocol: cTBS vs. iTBS] repeated-measures ANOVA.

**Statistical
Methodology**

Aim 2: Outcome measures. Accuracy and reaction time during the Sternberg Working memory paradigm. Statistical Analysis. The main analysis will be a 3 [stimulation: pre-stimulation vs. post-active vs. post-sham] by 2 [protocol: cTBS vs. iTBS] repeated-measures ANOVA.

Aim 3: Outcome measures. TMS-evoked BOLD activity during periods of acute fear and sustained anxiety. Statistical Analysis. BOLD maps will then be analyzed using a paired-sample t-test to compare BOLD responses evoked by active TMS and those evoked sham scalp stimulation.

**Data and Safety
Monitoring Plan**

The Principal Investigator is responsible for detecting, documenting, and reporting unanticipated problems (UPs), adverse events (AEs), including serious adverse events (SAEs), and deviations in accordance with IRB requirements and federal regulations.

CONFIDENTIAL

BACKGROUND AND STUDY RATIONALE

This study will be conducted in full accordance all applicable University of Pennsylvania Research Policies and Procedures and all applicable Federal and state laws and regulations including [as applicable include the following regulations as they apply 45 CFR 46, 21 CFR Parts 50, 54, 56, 312, 314 and 812 and Good Clinical Practice. All episodes of noncompliance will be documented.

Introduction

1.1 Background and Relevant Literature

Although anxiety disorders are the most commonly diagnosed class of disorders, with 1 in 5 individuals diagnosed annually, less than 50% of these patients receive treatment, and less than 15% receive minimally adequate treatment (Kessler & Chiu, 2005). Although extensive research has linked subcortical structures like the amygdala and bed nucleus of the stria terminalis (BNST) to the hyperarousal symptoms experienced by anxiety patients, hyperarousal is only one facet of the symptom profile shared across anxiety disorders. Much less is known about the cognitive symptoms (i.e. difficulty concentrating) experienced by anxiety patients. Given the low level of understanding of basic anxiety mechanisms, it is understandable that the most commonly used pharmacological treatments (e.g. benzodiazepines and SSRIs) for anxiety were developed more than 20 years ago, with little advancement since. Accordingly, there is a critical need for mechanistic research into the CNS mechanisms that mediate the cognitive symptoms experienced by anxiety patients. Without such research, treatment development for these disorders will continue to be slow.

TMS is approved by the FDA as a second-line treatment for depression (Horvath, Mathews, Demitrack, & Pascual-Leone, 2010; O'Reardon et al., 2007; Shajahan et al., 2002; Stern, Tormos, Press, Pearlman, & Pascual-Leone, 2007), and some studies have shown that TMS can reduce comorbid symptoms of anxiety in depressed individuals (Mantovani, Aly, Dagan, Allart, & Lisanby, 2013; O'Reardon et al., 2007; White & Tavakoli, 2015). TMS uses a strong and alternating magnetic field at the scalp to induce electrical currents in neurons just below the TMS coil. Theta-burst stimulation (TBS), where high frequency bursts (50 hz triplets) are delivered at the theta frequency (5 Hz), is capable of altering the resting membrane potentials of local neurons (Lefaucheur et al., 2014). Continuous TBS (cTBS) tends to decrease local excitability, while intermittent TBS (iTBS) tends to increase local excitability (Lefaucheur et al., 2014). TMS treatment protocols for depression are based on the hypothesis that the left dIPFC is associated with positive thoughts, and is hypoactive in depression (Berman, Doran, Pickar, & Weinberger, 1993; Galynker et al., 1998; Miller, Crocker, Spielberg, Infantolino, & Heller, 2013), while the right dIPFC is associated with negative thoughts and is hyperactive in depression (valence model) (Davidson, 2004). Thus, successful rTMS treatments for depression typically involve either excitatory rTMS to the left dIPFC or inhibitory rTMS to the right dIPFC (Chen et al., 2013; Concerto et al., 2015; Fox, Buckner, White, Greicius, & Pascual-Leone, 2012; Horvath et al., 2010; Lefaucheur et al., 2014; Miniussi et al., 2005; Nauczyciel et al., 2011; O'Reardon et al., 2007; Shajahan et al., 2002; Stern et al., 2007) (or both), however other paradigms have also shown benefit (e.g. excitatory of both right and left dIPFC).

There is evidence that rTMS treatment protocols (based on the valence model) may be effective at treating anxiety symptoms comorbid with depression. For instance, excitatory stimulation to the left dIPFC (O'Reardon et al., 2007), inhibitory stimulation to the right dIPFC (Mantovani et al., 2013), and combined *right* inhibitory rTMS and *left*

CONFIDENTIAL

excitatory rTMS to the dIPFC (White & Tavakoli, 2015) can reduce anxiety or panic in depressed individuals. However, several recent meta-analyses have concluded that there is little support for the efficacy of these treatments for anxiety reduction in non-depressed individuals (Lefaucheur et al., 2014; Pallanti & Bernardi, 2009; Pigot, Loo, & Sachdev, 2008; Zwanzger, Fallgatter, Zavorotnyy, & Padberg, 2009). One possible reason for this lack of support is that the underlying neuropathology mediating generalized anxiety and depression-related anxiety is fundamentally different (Baeken et al., 2010; Moulier et al., 2016; Zwanzger et al., 2014), suggesting a need for the development of novel, anxiety-specific rTMS treatment parameters. For instance, although excitatory stimulation to the left dIPFC facilitates retrieval of positive information in high anxious individuals (Balconi & Ferrari, 2012, 2013a, 2013b), excitatory stimulation to the left dIPFC does not reduce anxiety in non-depressed individuals (Moulier et al., 2016). Similarly, treatment with inhibitory stimulation to the right dIPFC enhances rather than suppresses subsequent visual processing of fearful stimuli (Zwanzger et al., 2014), while excitatory stimulation to the right dIPFC reduces subsequent amygdala activity to negative faces (Baeken et al., 2010). Taken together, these results suggest that the valence model may not be sufficient to explain the symptoms of anxiety in non-depressed individuals.

Instead, we propose a novel hypothesis based on the frontoparietal attention network (FPN; Figure 1) (Cole, Repovš, & Anticevic, 2014). According to our model, 1) elevated state anxiety enhances bottom-up attentional processes, and 2) top-down cognitive control processes, mediated by the right dIPFC, counteract this enhancement, reducing anxiety. This model is an extension of the attention control theory, which states that anxious individuals cannot efficiently engage goal-directed attention (Eysenck, Derakshan, Santos, & Calvo, 2007). Support for this model comes from the observations that 1) the right dIPFC plays a key role in attention control (Basten, Stelzel, & Fiebach, 2012; Cieslik et al., 2013; Fales et al., 2008; Harding, Yücel, Harrison, Pantelis, & Breakspear, 2015; Peers, Simons, & Lawrence, 2013), and 2) anxiety patients are impaired in their ability to recruit this structure for cognitive control (Armstrong, Zald, & Olatunji, 2011; Berggren & Derakshan, 2013a, 2013b; Braver, Cole, & Yarkoni, 2010; Coombes, Higgins, Gamble, Cauraugh, & Janelle, 2009; Derryberry & Reed, 2002; Eysenck et al., 2007; Grillon, Robinson, Mathur, & Ernst, 2015; Morrison & Heimberg, 2013; Najmi, Kuckertz, & Amir, 2012; Najmi, Amir, Frosio, & Ayers, 2014; Price, Eldreth, & Mohlman, 2011; Reinholdt-Dunne, Mogg, & Bradley, 2009, 2012). This model is also supported by recent studies and preliminary data from our lab that suggest, 1) cognitive tasks that occur during periods of elevated state anxiety recruit the right dIPFC, 2) tasks that engage the right dIPFC reduce state anxiety ([name], Quispe-Escudero, et al., 2016; Vytal, Cornwell, Arkin, & Grillon, 2012; Vytal, Cornwell, Letkiewicz, Arkin, & Grillon, 2013), 3) anxiety patients are less able to recruit the right dIPFC during demanding cognitive tasks ([name], Vytal, et al., 2016). Therefore, according to our model, we expect that enhancing activity in the right dIPFC with excitatory iTBS should facilitate top-down cognitive control processes associated with anxiety reduction. In addition, data suggest that activating the stimulation site via task engagement can facilitate the effect of rTMS (Luber et al., 2007, 2008, 2013), suggesting that rTMS during a challenging cognitive task may be more effective at anxiety reduction than rTMS alone.

[figure not shown]

Figure 1. R dIPFC may regulate anxiety through top-down inhibition of regions in the fear/anxiety circuit.

This research is significant because upon completion, we expect to have direct evidence for a causal role of the right dIPFC in anxiety regulation, complete with evidence

CONFIDENTIAL

of target engagement through simultaneous TMS/fMRI, and a novel application to anxiety. This research will lay the groundwork for my long-term career objective, which is to develop an independent, NIH-funded research program employing psychophysiology, neuroimaging, and neuromodulation in healthy and anxious participants aimed at developing a circuit-level understanding of the neurobiological mechanisms underlying anxiety.

2 Study Objectives

Aim 1: Determine the effect of a 1-week course of TBS treatment (Continuous vs. Intermittent; right dlPFC target) on anxiety using the unpredictable shock-threat paradigm. Our hypothesis, consistent with our pilot data, is that strengthening circuits in the right dlPFC will facilitate anxiety regulation. Accordingly, we expect excitatory but not inhibitory TBS (compared to sham) to reduce induced anxiety.

Aim 2: Determine the effect of a 1-week course of TBS treatment (Continuous vs. Intermittent; right dlPFC target) on anxiety-related WM-deficits using the Sternberg WM paradigm during threat of shock. Our hypothesis is that the rTMS will strengthen right dlPFC circuits, which will rescue the anxiety-related WM deficits. Accordingly, we expect that 10 Hz rTMS (compared to sham) will improve accuracy on the Sternberg WM task during threat.

Aim 3: Demonstrate target engagement by measuring BOLD responses evoked by TMS pulses to the right dlPFC during threat of shock. Our hypothesis is that direct stimulation of the right dlPFC will reduce ongoing anxiety-related activity. Accordingly, we expect active but not sham TMS pulses to the right dlPFC to evoke BOLD deactivations in regions of the fear/anxiety network (i.e. amygdala, BNST, anterior insula).

3 Investigational Plan

3.1 General Design

Aims 1 and 2 of this project will be tested using a between-subjects design where 1 group of healthy volunteers will receive 4-day courses of active and sham cTBS stimulation to the right dlPFC, while the other group will receive 4-day courses of active and sham iTBS stimulation to the right dlPFC. In Aim 1, we will test the effects of this stimulation on anxiety during the NPU threat task. In Aim 2, we will test the effects of this stimulation on anxiety-related WM deficits using the Sternberg WM paradigm. In addition, we will also administer several self-report questionnaires to assess their baseline (pre-stimulation) anxiety. Subjects will be randomly assigned to groups, and the order of stimulation (active vs. sham) will be counterbalanced across subjects. Aim 3 will be tested using a within-subjects design where this same group of subjects will receive single-pulse active and sham stimulation to the right dlPFC during the NPU threat task while in the MRI scanner. BOLD activity to the TMS pulses will be the primary outcome measure.

Subjects will undergo 12 study visits spaced over a 4-week period (Figure 3). Subjects may also be offered an optional 13th visit where TMS/fMRI is conducted. On Week 1,

CONFIDENTIAL

subjects will undergo a pre-stimulation behavioral visit where they complete the NPU threat task and the Sternberg WM paradigm, and a pre-stimulation MRI visit where they undergo all the structural and functional imaging needed to identify the optimal target of stimulation for the course of TMS used in Aims 1 and 2. This information will be used to perform neuronavigation during the study visits to ensure accurate target stimulation. Subjects will complete the TMS/fMRI scans needed for Aim 3 during the optional visit. On Weeks 2 and 4, subjects will undergo 5 visits. The first 4 visits will be stimulation visits where they receive either active or sham stimulation while doing the Sternberg WM task. On the 5th visit, they will return for the post-stimulation test visit, where they will complete the NPU threat task and the Sternberg WM paradigm.

[figure not shown]

Figure 3: Timeline showing subject visits in the proposed project.

3.1.1 Screening Phase

Participants will be recruited from the community via paper or web ads, flyers, and listserv announcements. Participants will be recruited without any preference based on gender, race, religion, or other social variables. All recruitment materials (paper or web ads, flyers and listserv announcements) will be IRB approved prior to use.

Study members authorized by the IRB will obtain informed consent from the participant. All study investigators obtaining informed consent complete formal informed consent training. All participants will receive a verbal explanation in terms suited to their comprehension of the purposes, procedures and potential risks of the study and of their rights as research participants. Participants will have the opportunity to carefully review the written consent form and ask questions regarding this study prior to signing. Consent forms will be signed in the presence of a witness.

Subjects will be informed that they can withdraw from the study whenever they wish. The experiment will also be stopped for any subject who exhibits signs of distress during any phase of the study. Subjects will be constantly monitored by the study staff. The subject will be withdrawn at any time if unable to follow the rules for participation in this study. In the event of unanticipated problems or serious side effects, the principal investigator will consider whether the study should continue.

3.2 Study Endpoints

Aim 1: Determine the effect of a 1-week course of rTMS TBS treatment (Continuous vs. Intermittent; right dIPFC target) on anxiety using the unpredictable shock-threat paradigm. Our hypothesis, consistent with our pilot data, is that strengthening circuits in the right

CONFIDENTIAL

dIPFC will facilitate anxiety regulation. Accordingly, we expect excitatory but not inhibitory TBS (compared to sham) to reduce induced anxiety.

Aim 2: Determine the effect of a 1-week course of rTMS TBS treatment (Continuous vs. Intermittent; right dIPFC target) on anxiety-related WM-deficits using the Sternberg WM paradigm during threat of shock. Our hypothesis is that the rTMS will strengthen right dIPFC circuits, which will rescue the anxiety-related WM deficits. Accordingly, we expect that iTBS (compared to sham) will improve accuracy on the Sternberg WM task during threat.

Aim 3: Demonstrate target engagement by measuring BOLD responses evoked by TMS pulses to the right dIPFC during threat of shock. Our hypothesis is that direct stimulation of the right dIPFC will reduce ongoing anxiety-related activity. Accordingly, we expect active but not sham TMS pulses to the right dIPFC to evoke BOLD deactivations in regions of the fear/anxiety network (i.e. amygdala, BNST, anterior insula).

4 Study Population and Duration of Participation

Participants will be recruited without any preference based on gender, race, religion, or other social variables, and participants will not be excluded on the basis of sex/gender, racial, or ethnic affiliation. We exclude pregnant women because of the unknown effects of the TMS pulses, shocks, and fMRI on the developing fetus. We exclude non-English speakers since not all the instruments and tests we use are translated and validated in Spanish or other languages.

4.1 Inclusion Criteria

- Subjects must be 18-50 years old
- Able to give their consent
- Right-handed

4.2 Exclusion Criteria

- Non-english speaking
- Any significant medical problems
- Current or past Axis I psychiatric disorder(s),
- Active or history of active suicidal ideation
- Alcohol/drug problems in the past year or lifetime alcohol or drug dependence
- Medications that act on the central nervous system
- History of seizure
- History of epilepsy or other neurological problems
- Increased risk of seizure for any reason
- Pregnancy
- Any medical condition that increases risk for fMRI or TMS
- Any metal in their body which would make having an MRI scan unsafe
- Any sort of medical implants
- Hearing loss

CONFIDENTIAL

- Claustrophobia

4.3 Subject Recruitment

Participants will be recruited from the community via paper or web ads, flyers, and listserv announcements. Participants will be recruited without any preference based on gender, race, religion, or other social variables. All recruitment materials (paper or web ads, flyers and listserv announcements) will be IRB approved prior to use.

In order to facilitate the enrollment of interested subjects in multiple studies at the Center for Neuromodulation in Depression and Stress (CNDS), we utilize a general pre-screening form (either administered by phone or self-report depending on participant preference) center-wide as the majority of our projects closely relate, in both purpose and eligibility criteria.

4.4 Duration of Study Participation

The study will consist of 12 study visits and take place over a period of approximately 4 weeks depending upon subject availability. Subjects may also be offered 3 optional visits. TMS/fMRI will be conducted during the first optional visit. The NPU will be administered before and after cTBS during the second and third optional visits. If subjects choose to participate in the optional visits. Their study participation will be extended approximately 1 week, according to their schedule. Each session will last approximately 2-3 hours.

4.5 Total Number of Subjects and Sites

The target number of completers will be N=56. We anticipate that about 20% of subjects (N=11) will terminate the study during the task because of discomfort and another 10% (N = 5) to withdraw due to scheduling issues. An additional 3 subjects per experiment (n=3) will be included for piloting.

4.6 Vulnerable Populations:

All subjects must be able to provide their own consent. This study is above minimal risk and we do not want to enroll participants who do not understand the risk/benefit ratio of the study, particularly when there is no benefit to the participants. For this reason we exclude people with IQ lower than 80. We exclude and rule out pregnant women because of the unknown effects of the shocks and of the fMRI on the developing fetus. We exclude non-English speakers since not all the instruments and test we use are translated and validated in Spanish or other languages. Based on our experience, we made the decision that 50 would be the upper age limit to prevent age-related changes in brain structure and function from confounding our analyses. Patients will not be taken off medications for the purpose of the study.

CONFIDENTIAL

5 Study Procedures

Does your study use MRI? (CAMRIS is the appropriate contact for all studies involving MRIs)

Yes No

Check of all that apply:

1.5T MRI
 3T MRI
 7TMRI

Does the MRI use investigational sequences and/or coils?
(See Experimental Device Clause)

Yes No Unsure (if unsure you need to contact CAMRIS)

Experimental Device Clause -- Some of the pulse sequences and/or RF coils are not FDA approved but are considered to pose no more than minimal risk.

Does your study include pregnant women?
(See Pregnancy Clause and Justification)

Yes No

Pregnancy Clause -- Although there are no known risks related to MRI on pregnant women or a fetus, there is a possibility of yet undiscovered pregnancy related risks. Since there is no possible benefit from participating in this protocol for a pregnant woman, we will exclude pregnant women.

Does the MRI require the use of Contrast Agents?
(See Contrast Risks)

Yes No

Does your study involve the exposure to radiation, radiotracers and/or radiological imaging modalities?

Yes No (If No, no RRSC review is needed)

Will any of the radiation exposure result from procedures that are or could be performed solely as a result of a subject's participation in the research protocol?

Yes No

CONFIDENTIAL

Ultrasound

Yes

No

Will your study be using CT Scans? (CACTIS is the appropriate contact for studies involving CT scans)

Yes

No

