6.2 Sample Size and Power Determination

Because we have several outcome measures, and because there is little known about how TMS will affect these outcome measures, we are conducting a single power analysis to determine sample size, based on a moderate effect size of ($f=0.5$). If we set power at 0.8 and use a corrected two-tailed alpha of 0.025 we would need 26 subjects per group to detect a main effect. Assuming a 15% unusable data rate and 3 pilot subjects, we will need 63 total subjects. However, this will be updated prior to enrollment based on the best available information at the time. To ensure that we are adequately powered across the study arms, and to account for additional dropout due to scheduling issues, we plan to recruit up to 75 participants.

7 Safety and Adverse Events

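### Section 4.5's loss counts (11 and 5) do not match its 20% and 10% on the 72 non-pilot recruits, and section 6.2's 63 should be 65 (minor, text only)

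*Combined protocol and SAP*

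**What the plan says.** Section 4.5 of the combined protocol and SAP states: "The target number of completers will be N=56". It then anticipates that "about 20% of subjects (N=11) will terminate the study during the task because of discomfort and another 10% (N = 5", the second group because of scheduling. On pilots it says: "An additional 3 subjects per experiment (n=3) will be included for piloting". It gives neither a recruitment total nor the base to which the percentages apply.

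Section 6.2 reaches its number separately. For an effect size of f = 0.5, power 0.8 and a corrected two-tailed alpha of 0.025, it says "we would need 26 subjects per group to detect a main effect", which is 52 in two groups. It continues: "Assuming a 15% unusable data rate and 3 pilot subjects, we will need 63 total subjects". It adds that "this will be updated prior to enrollment based on the best available information at the time", and closes by saying that, for adequate power across the arms and "to account for additional dropout due to scheduling issues, we plan to recruit up to 75 participants". The Study Summary repeats the total: "Number of Subjects 75".

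Section 7.5.1 says that pilots, subjects who withdraw and subjects with an adverse event are left out of the final analysis.

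**The concern.** Losses occur among people who enrol, so a loss rate has to be applied to the number enrolled. Section 4.5 appears to apply its two rates to the completers, who by definition are not lost, and then to add the result on top. That understates the loss that the rates imply. Section 6.2 appears to do the same with its 15%.

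At stake is whether the stated numbers can be relied on. A reader cannot tell from section 4.5 whether the planned attrition is 30% or 22%, or whether 75 recruits are expected to leave 56 completers or about 51. Those monitoring the study would have no single planned rate against which to compare observed dropout.

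**Working it through.** **Inputs.** Section 4.5: 56 completers; losses of 20% (11) and 10% (5); 3 pilots. Section 6.2: 26 per group, so 2 × 26 = 52; 15% unusable data; 3 pilots; 63 in total; cap of 75. Study Summary: 75.

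**Reproducing the plan's figures**

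- Section 4.5 counts: 0.20 × 56 = 11.2, printed as 11; 0.10 × 56 = 5.6, printed as 5 (truncated, since rounding would give 6).
- Total: 56 + 11 + 5 + 3 = 75, the figure in section 6.2 and the Study Summary.
- Section 6.2: 52 × 1.15 = 59.8, rounded up to 60; 60 + 3 = 63.

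**Section 4.5 on the enrolled base**

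Non-pilot recruits: 75 − 3 = 72.

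| | Discomfort | Scheduling | Together |
|---|---|---|---|
| Stated percentage | 20% | 10% | 30% |
| That percentage of 72 | 14.4 | 7.2 | 21.6 |
| Stated count | 11 | 5 | 16 |
| That count as a share of 72 | 15.3% | 6.9% | 22.2% |

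Expected completers:

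- Percentages hold, losses added: 72 × 0.70 = 50.4.
- Percentages hold, losses in sequence: 72 × 0.80 × 0.90 = 51.8.
- Counts hold: 72 − 16 = 56.
- Even if the 3 pilots counted as ordinary recruits, the percentages would give 75 × 0.70 = 52.5 or 75 × 0.72 = 54.0, still below 56.

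To leave 52 of 72, the total loss can be at most 1 − 52/72 = 27.8%. The two versions of the plan's loss (30% and 22.2%) lie on either side of that line. If the 20% and 10% losses are taken in sequence, the combined loss is 28% and the result is 51.8, in effect 52.

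**Section 6.2 with the rate applied to those enrolled**

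- Check of the stated figure: 60 × 0.85 = 51, one short of 52.
- Correct inflation: 52 / 0.85 = 61.2, rounded up to 62; 62 + 3 = 65.

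**Does this threaten power?** As a stress test, apply the 15% on top of the lowest completer figure: 50.4 × 0.85 = 42.8, about 43. Power at f = 0.5 and alpha 0.025:

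| N | Stimulation effect or interaction, 3 × 2 repeated-measures ANOVA | Plain two-group comparison (d = 1.0) |
|---|---|---|
| 43 | 0.968 | 0.825 |
| 50 | 0.987 | 0.885 |
| 52 | 0.990 | 0.898 |

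The ANOVA column assumes sphericity, error df = (N − 2) × 2 and noncentrality = f² × error df, because section 6.2 names no convention. The second column is a two-sided two-sample t-test.

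**The case against.** The best defence is that nothing in the design turns on this. Section 4.5 calls its rates approximate. Section 6.2 announces that its figure will be updated and moves straight on to 75, so 63 is not the operative number and the move to 65 is covered. Power stays above 0.80 in every row of the table. With section 6.2's 15% and a 10% scheduling loss alone, 72 recruits would leave 72 × 0.75 = 54.0 or 72 × 0.85 × 0.90 = 55.1, above 52. The count reading (11/72 = 15.3%) is also close to section 6.2's 15%, although the documents do not say that these are the same loss. Finally, the base of 56 is inferred: section 4.5 does not state it, and 5.6 has to be truncated to give 5.

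Most of this stands as to weight, and it keeps the point minor. It does not remove the error. An approximate 20% does not stretch to 15.3%, nor 10% to 6.9%, and whichever of counts or percentages was intended, a printed number is wrong. The promised update concerns section 6.2's figure and leaves section 4.5 untouched.

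Three stronger readings are tempting and are not supported:

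- *The trial is underpowered.* The table does not show this.
- *56 and 52 contradict each other.* One is a target for completers and the other a required minimum. A target above a minimum is not a contradiction.
- *Recruitment must rise to 81–83.* That follows (56/0.72 = 77.8, so 78, plus 3; or 56/0.70 = 80, plus 3) only if both 56 and the percentages are kept, and the documents do not say that both are firm. Against 52 the same rates need 76–78 (73 + 3 or 75 + 3), which is 1–3 above the cap.

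**Conclusion.** The arithmetic point holds and is minor. The counts and percentages in section 4.5 cannot both describe losses among the 72 non-pilot recruits. At the stated percentages 75 recruits give about 50 to 52 completers, which is 4 to 6 fewer than 56 and at or just under section 6.2's 52. At the stated counts 56 is right and the rates are about 15% and 7%. The documents do not say which is the planning assumption. Section 6.2's 63 should be 65.

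Section 6.2 also leaves open whether its 15% overlaps with the losses in section 4.5. That is a missing link between the sections, not a further arithmetic error.

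The result assumes that the 3 pilots are inside the 75, as the sum implies, and takes 26 per group as given. No figure here is a forecast of analysable subjects: section 7.5.1 also excludes anyone with an adverse event, and the plan gives no overall rate for that. For the same reason, the power values show only that this arithmetic does not bring power below 80%; they do not settle the final analysed number.

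**What to change.** Change the text only; no extra subjects or visits are needed.

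**Section 4.5.** State that losses are counted among the 72 non-pilot recruits, then choose one:

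- (a) If the percentages are the assumption: keep 20% and 10%, change the counts to about 14 and 7, and give about 50–52 expected completers in place of 56.
- (b) If the counts are the assumption: keep 11, 5 and 56, and change the percentages to about 15% and 7%.

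Do not simply substitute 52 for 56. The 52 is section 6.2's minimum, and nothing in the documents supports adopting it as the completer target.

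**Section 6.2.** Replace 63 with 65 (52/0.85, rounded up to 62, plus 3). Add one sentence saying whether the 15% unusable rate lies within the losses in section 4.5 or adds to them. Do not insert expected numbers of usable subjects, because the adverse-event exclusion in section 7.5.1 is not quantified.

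**Cost.** A few words in two sections. Under (a) the expected number of completers looks slightly less favourable, at or just under 52.
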